Any contraindications or cardiovascular risk factors	Potential confounder	Ever experienced any contraindications or cardiovascular risks factors listed above
Time since migraine diagnosis	Potential confounder	Time since migraine diagnosis in years
Monthly migraine days (continuous)	Potential confounder	Number of days experienced migraine in past 30 days
Monthly headache days (continuous)	Potential confounder	Number of days experienced headache in the past 30 days
Medication overuse (migraine only)	Potential confounder	Yes or no, for migraine-specific medications only
Other covariates that will be evaluated for balance between exposure groups		
Age (categorical)*	Potential confounder	Categorized based on age of participants in years: 18-29, 30-39, 40-49, 50-59, 60-69, 70-79, 80-89
Monthly migraine days (categorical)*	Potential confounder	Categorized based on number of days experienced migraine in past 30 days: <4, 4-9, 10-14, and \geq 15
Monthly headache days (categorical)*	Potential confounder	Categorized based on number of days experienced headache in past 30 days: <4, 4-9, 10-14, and \geq 15
Experience migraines related to menstrual cycle	Potential confounder	Yes vs. no, female participants only

*Categorical age, monthly migraine days, and monthly headache days will be included in inverse probability of treatment weighting (IPTW) adjustment if their distributions are not balanced (standardized mean difference >0.1) after IPTW.

Abbreviations: OTC: over the counter; NSAID: non-steroidal anti-inflammatory drugs; CGRPs mAb: calcitonin gene-related peptide antibodies monoclonal antibodies; HRQoL: health related quality of life; PCS: physical composite score; MCS: mental composite score; GCS: global composite score; WPAI-GH: the Work Productivity and Activity Impairment – General Health; MIDAS: Migraine Disability Assessment Scale; HCRU: health care resource utilization; ER: emergency room; IPTW: inverse probability of treatment weighting

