9.7. Data Analysis

The average treatment effect of treated (ATT) will be measured to evaluate the effects of Rimegepant vs. triptan among current Rimegepant users.

Based on clinical relevance, we will prespecify a list of variables to adjust for the comparison.

Inverse probability of treatment weighting (IPTW) will be conducted to adjust for confounding by the covariates. The propensity score for each participant will be estimated by logistic regression and by including the prespecified list of variables to adjust for. Weights for ATT will be calculated for both exposed (Rimegepant users) and unexposed group (triptan users)¹⁶. Stabilized weights will be used to address extreme weight values.

To confirm that the IPTW procedure is successful, the weighted Rimegepant users and triptan users will be compared on the covariates using standardized mean difference (SMD) to ensure both groups are adequately balanced across all weighting criteria. While there is no definitive cut-off for identifying imbalance in IPTW, as a rule of thumb, a standardized mean difference (SMD) that is >0.10 is indicative of imbalance¹⁷. This threshold will be applied to determine the quality of the weighting.

Once the weighting is confirmed to be successful, bivariate analyses will be conducted to compare the weighted cohorts on treatment satisfaction, HCRU, QoL, migraine-specific

disability, and work productivity loss. Specifically, categorical variables will be analyzed using chi-square tests or Fisher's exact tests for small samples; continuous variables will be analyzed using 2-sample t-tests. Non-parametric tests may be considered for comparisons on skewed variables (e.g., HCRU) when the sample size is small (e.g., <30). For bivariate comparisons, p-values <0.05, 2-tailed, will be considered statistically significant. If there are covariates that are unbalanced after weighting (i.e., SMD >0.1), those covariates will be adjusted for in the regression analysis of outcomes. Generalized linear models will be fit depending on the distributions of outcomes.

As a sensitivity analysis, the aforementioned IPTW and bivariate comparisons will be replicated after restricting the Rimegepant user cohort to the subset of those presumed to be acute treatment users (<12 days using Rimegepant).

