A sensitivity analysis will be conducted by incorporating NHWS sampling weights into the IPTW process. Sampling weights will be applied in the logistic regression to predict the propensity score, and the final weight will be the product of the propensity score weight and the sampling weight. Bivariate comparisons will then be replicated after using these newly derived weights for the participants.

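### Section 9.7 lets an SMD threshold decide whether outcomes are covariate-adjusted and does not tie the adjusted result to the ATT; one fixed ATT-weighted, standardised estimator would be better

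*Combined protocol and SAP*

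**What the plan says.** Section 9.7 sets the target: "The average treatment effect of treated (ATT) will be measured to evaluate the effects of Rimegepant vs. triptan among current Rimegepant users". After ATT weighting, the default comparisons are bivariate. Categorical outcomes get chi-square or Fisher tests, and "continuous variables will be analyzed using 2-sample t-tests".

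Regression enters in two sentences. The first is "If there are covariates that are unbalanced after weighting (i.e., SMD >0.1), those covariates will be adjusted for in the regression analysis of outcomes". The second, "Generalized linear models will be fit depending on the distributions of outcomes", is all that defines the model.

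The footnote to Table 1 (Section 9.3) uses the same threshold differently. It says of three categorised variables (age, and headache and migraine days per month) that they "will be included in inverse probability of treatment weighting (IPTW) adjustment if their distributions are not balanced (standardized mean difference >0.1) after IPTW". The menstrual-cycle item is also checked for balance, but it is outside the weighting list, has no asterisk and is defined for women only. Regression is thus its only stated remedy.

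For the acute-user sensitivity analysis, "the aforementioned IPTW and bivariate comparisons will be replicated after restricting the Rimegepant user cohort". For the sampling-weight sensitivity analysis, "Bivariate comparisons will then be replicated after using these newly derived weights for the participants". Neither names a regression step.

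**The concern.** Whether an outcome gets an unadjusted weighted difference or a covariate-adjusted model depends on the balance observed, and the adjusted model contains only the covariates that crossed the line. Four problems follow.

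- **Undefined contrast.** With a logit or log link, or with effects that vary between patients, a model coefficient need not equal the ATT unless predictions are averaged over the Rimegepant users. The plan does not say that they will be.
- **Two remedies for one trigger.** The footnote re-weights and Section 9.7 regresses. No order is given.
- **Sensitivity analyses that may not match.** If the main analysis is adjusted, the analyses meant to corroborate it (Section 8) repeat only the unadjusted comparisons.
- **Error bars and residual imbalance.** Estimating the weights removes chance imbalance in prognostic covariates. An unadjusted weighted comparison that treats the weights as fixed takes no credit for this. Imbalance up to an SMD of 0.10 is also left in place, even for strong outcome predictors.

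Section 8 says the findings may support payer communications, so readers need to know which quantity each figure estimates and how precise it is.

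**Working it through.** **1. The plan's own figures (Section 9.5).** 130 per group at 0.35 SD gives 80.3% power (t-test). 100 per group at 0.4 SD gives 80.4%. Chi-square with effect size 0.33, N = 100 and 3 df gives 79.9%. All reproduce, and none is affected by this point.

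**2. Scale of the comparison.** Table 2 gives 144 or 112 Rimegepant users and 1,340 triptan users. In outcome-SD units and with no loss of effective sample size (ESS):
- SE = √(1/144 + 1/1,340) = 0.0877; detectable difference at 80% power = 2.80 × 0.0877 = 0.246 SD.
- SE = √(1/112 + 1/1,340) = 0.0984; detectable difference = 0.276 SD.

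**3. Bias the threshold can leave.** Take one covariate at an SMD of exactly 0.10 and an assumed correlation of 0.5 with the outcome. The bias is 0.10 × 0.5 = 0.05 SD, and 0.05/0.246 = 20% of the detectable difference. In SE units it is 0.05/0.0877 = 0.57. The two-sided 5% error becomes P(Z > 1.39) + P(Z > 2.53) = 8.2% + 0.6% = 8.8%. This is a ceiling for one covariate, not an expected value.

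**4. How often the switch fires.** For a covariate outside the propensity model with no true imbalance, P(|SMD| > 0.1) = 2[1 − Φ(0.1/SE)]:

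| Rimegepant n | Control ESS 1,340 | Control ESS 400 (assumed) |
|---|---|---|
| 144 | 25.4% | 30.3% |
| 112 | 30.9% | 35.0% |

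For covariates inside the model the rate depends on assumptions. It was 0-0.5% of runs with normal covariates and a correct propensity model. It was 5-26% (main) in a simulation with covariates shaped like Table 1. The documents cannot decide between these.

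**5. True and reported precision.** Simulation with about 1,484 people, 20 covariates in the propensity model, constant effect, and R² the share of outcome variance explained. Reported SEs are robust with weights treated as fixed.

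| Setting | True SE, unadjusted | True SE, always adjusted | Reported SE, unadjusted | Reported SE, adjusted |
|---|---|---|---|---|
| R² 0.4 | 0.097 | 0.097 | 0.126 | 0.092 |
| R² 0.4, stronger confounding | 0.100 | 0.098 | 0.122 | 0.090 |
| R² 0.2 | 0.095 | 0.095 | 0.108 | 0.092 |

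The true error hardly moves. The reported SE of the unadjusted comparison is too large by 0.126/0.097 = 1.30, 0.122/0.100 = 1.22 and 0.108/0.095 = 1.14. The adjusted fixed-weight SE is slightly too small, which is why the weights should be re-estimated in a bootstrap.

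A separate simulation with other assumed covariates gave the same pattern. The unadjusted comparison reported SEs of about 0.10-0.13 against a true 0.07-0.09, and its intervals covered 99-100%. Always adjusting for a fixed prognostic set cut the mean reported SE by about 30-38%, with 94-95% coverage and no added bias. Mean squared error fell by 0-13%.

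With a prognostic binary covariate left outside the propensity model, true SEs were 0.099-0.108 unadjusted, 0.096-0.097 with the switch and 0.093-0.094 always adjusted.

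**6. Scale for yes/no outcomes.** In the weighted simulation the odds ratio was 1.75-1.80 unadjusted, 1.80-1.81 with one extra covariate (a shift of about 1-3%) and 2.08-2.13 with all covariates. The difference matters only if many or strong covariates enter a logistic model and its coefficient is reported without standardising.

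**The case against.** Adjusting for what remains unbalanced after weighting is a prespecified safeguard, and the Table 1 confounders already enter through the propensity score. The footnote and Section 9.7 can be read as a sequence: re-weight first, then regress on what is left. The regression sentence could also mean a planned regression to which unbalanced covariates are added. The trigger rates, bias and simulated errors all rest on assumed covariates.

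Much of this stands, and it limits the point. A reader might infer three stronger things that the documents do not support:
- **That the plan reports a conditional coefficient in place of the ATT.** It does not say so; it is silent. With an identity link, retained ATT weights and good balance, the coefficient does target the ATT (simulated bias at most about 0.005 SD).
- **That much real precision is thrown away.** When the prognostic covariates are in a correct propensity model, the true SE is almost unchanged.
- **That the main and acute-user analyses will switch separately and disagree.** The sensitivity text contains no switch. What it lacks is any regression step.

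What the objection does not answer is that, on any reading, the contrast, the use of weights and the standard error are unstated. The order of the two remedies is not given, and a female-only item has whole-cohort regression as its only remedy.

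**Conclusion.** The point holds as a matter of specification and of choosing a better estimator. It is not an error in any stated figure. Section 9.7 lets a threshold choose between an unadjusted and a partly adjusted analysis, does not link the adjusted one to the ATT, and does not carry it into the sensitivity analyses.

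The main measurable cost is overstated uncertainty: reported SEs some 14-30% above the true value in the first simulation, and intervals covering 99-100% in the second. This assumes a robust SE with fixed weights; the plan names no SE method, and another choice would behave differently. The secondary cost is residual bias of up to about 0.05 SD per covariate at an assumed correlation of 0.5. The gain in true error from always adjusting is small. The change is worth making because it is cheap and gives every analysis the same defined quantity.

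**What to change.** In Section 9.7, replace the switch with one rule for the main and both sensitivity analyses:

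1. For each whole-cohort outcome, fit an ATT-weighted GLM with treatment plus a fixed set of prognostic covariates. Choose the set now from the Table 1 weighting list, use it in every analysis, and keep it short enough for the rarer yes/no outcomes with 112 Rimegepant users.
2. Average the predicted outcomes under each treatment over the Rimegepant users. Report the ATT mean, risk or rate difference.
3. Give a 95% CI from a bootstrap that re-estimates the propensity score and weights in each resample, or an equivalent SE.
4. Keep SMD > 0.1 as a diagnostic that leads to re-specifying the propensity model, in line with the Table 1 footnote. It should not choose the outcome method.
5. Assess and handle the menstrual-cycle item in women only.

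In choosing the set, note that migraine and headache days cover the past 30 days in current users, so treatment may already have affected them. The plan's propensity model has the same issue, and this change neither creates nor cures it.

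Cost: a paragraph in Section 9.7, a few more model terms and some R code for standardisation and the bootstrap. No new data are needed.

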9.8. Quality Control

This is a non-interventional retrospective study, so issues of quality control at study sites, e.g., data queries, do not apply. The following programming specifications will be used:

- NHWS survey includes single select questions, multi select multiple choice questions, as well as open-ended questions (e.g., asking participants to type in the types of over-the-counter medications they were taking).
- NHWS data to be used in this study will be downloaded from the Oracle server and saved as a separate data file. This data file will be stored in a secure folder on the Oracle server, which is backed up in multiple iterations on a regular basis.
- Programming code will be created for data management. This programming code will include the creation of cohort variables or any other derived variables.
- All analyses will be performed using R 4.3.1 (R Project for Statistical Computing). For quality assurance purposes, a second independent researcher will review the programming code to be used for analysis.
- Programming code used for data management and programming code used for analysis will be stored on the Oracle server and will be backed up on a regular basis.
- Data will be reviewed for quality control prior to data analysis by OLS. For example, if a respondent entered the same number for most responses, or followed a pattern in their responses, they would be considered for removal from analysis. In addition, prior to data analysis, all variables are cleaned and checked for outliers and inconsistencies by OLS.

9.9. Limitations of the Research Methods

The data from the NHWS are self-reported; thus, independent, or clinical verification of responses will not be possible. Due to the self-reported nature of the data, recall error or other response biases may potentially introduce measurement error. However, many of the measures included in the study were developed solely for the purposes of patient self-report (RAND-36, EQ-5D-5L, WPAI-GH, MIDAS), and self-report is a valid and appropriate methodology for assessing subjective outcomes. Because of the cross-sectional nature of the data, causal inferences cannot be drawn, and longitudinal fluctuations in the relationships between study variables cannot be determined. While IPTW will be used to control for potential confounders, it is possible there are other variables that could not be included in the analyses that may at least partially explain any relationships observed in the current study. Finally, while the NHWS is designed to reflect the demographic composition of the general adult population in each country in which it is fielded, it is possible that the data may not be representative of the specific patient subpopulations examined in this study.

9.10. Other Aspects

Not applicable.

10. PROTECTION OF HUMAN PARTICIPANTS

10.1. Patient Information

This study involves data that exist in deidentified/anonymized structured format and contain no patient personal information.

10.2. Patient Consent

As this study involves deidentified/anonymized structured data, which according to applicable legal requirements do not contain data subject to privacy laws, obtaining informed consent from patients by Pfizer is not required.

10.3. Institutional Review Board (IRB)/ Independent Ethics Committee (IEC)

IRB/IEC is not required for this study. However, the protocols and questionnaire associated with the original fielding of the 2023 US NHWS were reviewed by Pearl Institutional Review Board (Indianapolis, IN; Protocol Number: 2023-0121) and granted exemption from expedited or full ethical review. The granted exemption is stored on the Oracle server.

10.4. Ethical Conduct of the Study

The study will be conducted in accordance with legal and regulatory requirements, as well as with scientific purpose, value, and rigor and follow generally accepted research practices described in Good Practices for Outcomes Research issued by the International Society for Pharmacoeconomics and Outcomes Research (ISPOR)¹⁸.

11. MANAGEMENT AND REPORTING OF ADVERSE EVENTS/ADVERSE REACTIONS

This study involves data that exist as structured data by the time of study start. In these data sources, individual patient data are not retrieved or validated, and it is not possible to link (i.e., identify a potential association between) a particular product and medical event for any individual. Thus, the minimum criteria for reporting an adverse event (AE) (i.e., identifiable patient, identifiable reporter, a suspect product, and event) cannot be met.

12. PLANS FOR DISSEMINATING AND COMMUNICATING STUDY RESULTS

Study results will be disseminated in the form of abstract submissions and poster presentations at the American Academy of Neurology (AAN) meeting in May 2025. For all publications relating to the study, Pfizer will comply with recognized ethical standards concerning publications and authorship.

In the event of any prohibition or restriction imposed (e.g., clinical hold) by an applicable competent authority in any area of the world, or if the party responsible for collecting data from the participant (i.e., Oracle Life Sciences) is aware of any new information which might influence the evaluation of the benefits and risks of a Pfizer product, Pfizer should be informed immediately.

15. LIST OF FIGURES

Not applicable.

ANNEX 1. LIST OF STANDALONE DOCUMENTS

None.

